3. SPECIFIC AIMS

3.1 Overall Study Design and Plan

This is a single-site single crossover, double-blind placebo (PBO)-controlled randomized sequence block trial of nicotinamide riboside (NR, TruNiagen®, Chromadex) vs. PBO in 40 volunteers with SCD or MCI. All volunteers will receive a four-week PBO-lead in and acclimatization followed by two 8-week "blocks". Each block consists of either NR or PBO for an 8-week period in random assignment order. Outcomes will consist of standardized cognitive, neuropsychiatric, functional and biomarker assessments as well as daily cognitive, mood, sleep, and activity monitoring with computer-based brain games and wearable actigraphy. Due to the COVID-19 pandemic, some of the study visits will be completed fully or partially via Zoom videoconference to minimize the amount of contact between study staff and research subjects.

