4.1.2 Exclusion Criteria

A subject will not be eligible for study participation if they meet any of the following criteria

- Any specific CNS disease history other than suspected ADRD, such as major clinical stroke, brain tumor, normal pressure hydrocephalus, multiple sclerosis, significant head trauma with persistent neurological of cognitive deficits or complaints;
- 2) Any impairment in instrumental activities of daily living that would indicate a level of cognitive impairment beyond MCI as assessed by a trained rater;
- 3) Clinically significant unstable medical condition that could affect safety or compliance with the study and would, in the opinion of the investigator, pose a risk to the participant if they were to participate in the study;
- 4) History of neuroimaging with evidence of major infarction, injury, infection, or other focal lesions that may be related to cognitive dysfunction;
- 5) If participating in the optional LP sub-study, any contraindication to undergo lumbar punctures, such as:
 - a. Abnormal coagulation PT/INR test result, outside of the normal range of 0.9 to 1.2 platelet counts below 50,000 (interpreted by a licensed study physician or nurse practitioner after reading test results);
 - b. Platelet counts below 50,000;
 - c. Use of coumadin or other blood thinner medications;
 - d. Infection near the puncture site, or spinal column deformities (a licensed physician or nurse practitioner will examine the site visually for infection or spinal deformities before performing the procedure);
 - e. Known allergy to Lidocaine.
- 6) Major active or chronic unstable psychiatric illness (e.g. depression, bipolar disorder, obsessive compulsive disorder, schizophrenia) within the previous year;
- 7) Current suicidal ideation or history of suicide attempt;
- 8) History of alcohol or other substance abuse or dependence within the past two years;
- 9) Any significant systemic illness or medical condition that could affect safety or compliance with study;

A Crossover, Randomized Block Sequence, Double-Blind, Placebo-Controlled Trial for Nicotinamide Riboside in Subjective Cognitive Decline and Mild Cognitive Impairment in Aging
Version: 4.4

- 10) Laboratory abnormalities at Baseline in vitamin B12, thyroid stimulating hormone (TSH), or other common laboratory parameters that might contribute to cognitive dysfunction or other abnormalities in hematological, hepatic or renal function tests;

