5.4 Reasons for Withdrawal

A study subject will be discontinued from participation in the study if:

- Any clinical adverse event (AE), concurrent illness, or other medical condition or situation occurs such that continued participation in the study would not be in the best interest of the subject.
- The subject meets any exclusion criteria (either newly developed or not previously recognized).
- The subject is less than 80% or greater than 120% compliant with NR dosing.

Subjects are free to withdraw from participation in the study at any time upon request.

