5.5 Termination of Study

This study may be prematurely terminated if, in the opinion of the investigator, there is sufficient reasonable cause.

Circumstances that may warrant termination include, but are not limited to:

- Determination of unexpected, significant, or unacceptable risk to subjects.
- Unsatisfactory enrollment.
- Insufficient adherence to protocol requirements.
- Data that are not sufficiently complete and/or evaluable.

If the study is prematurely terminated or suspended, the investigators will promptly inform the institution and regulatory authorities of the termination or suspension and the reason(s) for the termination or suspension. The IRB/IEC will also be informed promptly and provided the reason(s) for the termination or suspension by the investigator, as specified by applicable regulatory requirement(s).

Version:4.4

A Crossover, Randomized Block Sequence, Double-Blind, Placebo-Controlled Trial for Nicotinamide Riboside in Subjective Cognitive Decline and Mild Cognitive Impairment in Aging

6. **STUDY PROCEURES**

6.1 **Schedule of Assessments**

	Days -28 to -1 Screening Visit ¹	Day 0 Lead-in	Day 28 ± 4 days Baseline	Day 56 ² ± 4 days Block 1 Midway	Day 84 ± 4 days Crossover (PBO/NR)	Day 112 ² ± 4 days Block 2 Midway	Day 140 ± 4 days End of Study	Day 154 ± 4 days Follow Up ¹	Early Termination
Informed Consent ^{1,3}	X								
Informed Consent Worksheet ¹	X		X		X		X		
Demographics ¹	X								
Medical History ^{1,4}	X	X	X	X	X	X	X	X	X
Height & Weight		X							
Vital Signs		X	X		X		X		X
Inclusion/ Exclusion Review ¹	X	X							
Safety Labs ⁵		X					X	X^6	X
Concomitant Medications & Supplements ¹	X	X	X	X	X	X	X	X	X
Physical & Neurological Examination		X	X		X		X		
Cognitive Screening Measures ^{1,7}	X								
Test of Premorbid Functioning		X							
Randomization		X							
Dispense Supplement/Placebo		X	X		X				
Accountability and Compliance			X	X	X	X	X		X

A Crossover, Randomized Block Sequence, Double-Blind, Placebo-Controlled Trial for Nicotinamide Riboside in Subjective Cognitive Decline and Mild Cognitive Impairment in Aging Version: 4.4
Version date: May 26, 2022

	Days	Day 0	Day 28	Day 56 ²	Day 84	Day 112 ²	Day 140	Day 154	Early
	-28 to -1		± 4 days	± 4 days	± 4 days	± 4 days	± 4 days	± 4 days	Termination
	Screening Visit ¹	Lead-in	Baseline	Block 1 Midway	Crossover (PBO/NR)	Block 2 Midway	End of Study	Follow Up ¹	
Virtual Cognitive Assessment ^{1,8}			X		X		X		X
Virtual Neuropsychiatric Surveys ^{1,9}			X		X		X		X

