6.1.2 Lead-In Visit (Day 0)

This visit will take place within 28 days of the Screening Visit. The following procedures will be performed and will take approximately 1.5 hours.

The following procedures will take place at the in-person office visit:

- Measure Vital Signs
- Physical and Neurological examination
- Blood draw for safety labs and biomarker analysis
- Dispense PBO
- Explain and practice how to use technological devices and software that will be used during study-computer, daily Lumosity brain games, Fitbit device, Fitbit software.
- Administer TOPF
- Assess inclusion and exclusion criteria to determine subject eligibility

6.1.2.1 Technology Check-In Phone Calls- Days 1, 7, and 21

At Days 1, 7, and 21 (± 1 day) during the initial Lead-in Period, a study coordinator will call the subject to ensure they understand how to use all technology and discuss compliance if necessary. The subjects will also be provided with the study coordinator's phone number and email and encouraged to contact the study coordinator with questions or concerns at any time.

A Crossover, Randomized Block Sequence, Double-Blind, Placebo-Controlled Trial for Nicotinamide Riboside in Subjective Cognitive Decline and Mild Cognitive Impairment in Aging

Version:4.4

6.1.3 Baseline Visit (Day 28), Crossover Visit (Day 84), and End of Study Visit (Day 140)

These visits will occur 28 days (\pm 4 days) after the previous visit. These visits will occur in two parts: the first portion will occur virtually via Zoom videoconference no more than 4 days prior to the second portion, which will be an office visit. The following procedures will be performed and will take approximately 2.5-6 hours depending on participation in LP and MRI sub-studies. If the subject has elected to participate in the LP and/or MRI sub-study, the visit may occur over multiple days as long as all tasks are completed during the study visit window.

The following measures will be performed virtually via Zoom videoconferencing no more than 4 days prior to the office visit:

- Assessment of capacity to consent through administration of the Informed Consent Worksheet
- Administer cognitive assessments
- Administer functional and mood assessments
- Assess technology compliance
- Assess and document AEs and changes to medical history
- Review and document concomitant medications, supplements, and therapies

The following procedures will occur in person:

- Measure Vital Signs

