9. STATISTICAL ANALYSIS

9.1 Biostatistical analysis

This is a crossover randomized controlled trial with the goal of determining the effects of a potential cognitionenhancing dietary supplement for older adults with SCD and MCI. The primary analysis will be based on an intention to treat approach and will include all subjects randomized at the onset of the trial to either NR then placebo or placebo then NR as described below.

In this study, the participants will pass through intervention blocks with administration of both NR and PBO for eight weeks administered in random order. The primary cognitive outcome measure will be the Total Scale score of the RBANS which will be administered at Baseline (Day 28), Crossover (Day 84), and End of Study (Day 140). The RBANS is a robust 25-minute, standardized neurocognitive battery with multiple alternate versions whose 12 subtests yield five Index scores, one for each cognitive domain, and the Total Scale score.

A Crossover, Randomized Block Sequence, Double-Blind, Placebo-Controlled Trial for Nicotinamide Riboside in Subjective Cognitive Decline and Mild Cognitive Impairment in Aging

Version:4.4

Normative data have been published for cognitively normal older adults, as well as for MCI and AD populations. For example, in a study of MCI, the mean Total Score Index was reported to be 92.4 with a standard deviation of 9.1⁴³. Based on test-retest reliability, a minimal detectable change in community-dwelling older adults (including normal, MCI and mild dementia) for the Total Score is 5⁴³. A "minimum clinically important difference" in MCI was reported to be 8 points⁴⁴.

The basic data of a crossover trial are the measurements obtained in 2 or more different intervention conditions occurring over time. The principal goal is to compare outcomes for each condition within a randomized block structure while accommodating repetition *within* subjects and possible effects of carryover or disease progression.

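### Randomisation is scheduled 28 days before the allocation or the first RBANS is needed, and 5.4 ends RBANS collection for non-compliers, so the all-randomised analysis set in 9.1 cannot be fully observed (minor)

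*Combined protocol and SAP*

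**What the plan says.** **Timing.** In the Schedule of Assessments (6.1) the row "Randomization" is marked under Day 0, the Lead-in visit. Section 3.1 states: "All volunteers will receive a four-week PBO-lead in and acclimatization". The Day 0 list in 6.1.2 dispenses placebo only and includes "Blood draw for safety labs and biomarker analysis". These are the only safety labs scheduled before Block 1. The RBANS is scheduled at Days 28, 84 and 140 (3.2.1, 7.1.2.2.3) and at Early Termination (6.1).

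**Eligibility.** Exclusion 10 (4.1.2) covers "Laboratory abnormalities at Baseline in vitamin B12, thyroid stimulating hormone (TSH), or other common laboratory parameters that might contribute to cognitive dysfunction", although the labs are drawn at Day 0 and Baseline is Day 28. Under 5.4, "A study subject will be discontinued from participation in the study if" any of several conditions applies. One of them is "The subject meets any exclusion criteria (either newly developed or not previously recognized").

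**Compliance.** Another condition in 5.4 is: "The subject is less than 80% or greater than 120% compliant with NR dosing". Section 8.5 sets the same limits for the study product in general. It calls for retraining first and leaves discontinuation to the principal investigator if the problem persists.

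**Analysis.** Section 9.1 defines an intention-to-treat analysis that "will include all subjects randomized at the onset of the trial to either NR then placebo or placebo then NR". It names a matched-pair t-test, and a mixed model with sequence and treatment effects in which Days 28, 84 and 140 each count as the end of a period. It gives no rule for a randomised subject without an RBANS.

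**The concern.** An all-randomised analysis needs the primary outcome to be obtainable from everyone randomised. Two provisions work against this.

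1. Allocation is made four weeks before it is used. Anyone who leaves in those weeks, including a subject whose Day 0 lab results come back disqualifying, is in the denominator with no RBANS. The order of blood draw, eligibility review and randomisation within Day 0 is not stated, nor is lab turnaround. The Early Termination visit does not help here, because 6.1.6 offers it only after Baseline.
2. Removal from the study for poor compliance turns a treatment-adherence problem into missing outcome data. Adherence after Day 28 may depend on the product taken, so this loss is less innocent than a lead-in loss.

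At stake are a clean denominator, the balance between sequences, and some precision.

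**Working it through.** The plan gives no loss rate and no calculation on this point, so there is no figure to reproduce. The loss rates, 40 randomised (20 per sequence) and the within-subject correlations below are assumptions. The 40 comes from 3.1, but 4.2 may mean 40 completers.

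**Step 1: lead-in losses.** Randomised subjects with no RBANS = 40 × p. For p = 2%, 5%, 10% and 15% this is 0.8, 2, 4 and 6.

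**Step 2: effect on the estimate.** With n1 and n2 left in the two sequences, the unadjusted paired difference shifts by period effect × (n1 − n2)/(n1 + n2). Two losses from one sequence and an assumed 2-point period effect give 2 × (20 − 18)/38 = 0.105 points. Section 9.1 quotes a minimal detectable change of 5.

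**Step 3: removals, paired t-test.** Two to four lost pairs (5% to 10% of 40) raise the standard error by √(40/38) − 1 = 2.6% to √(40/36) − 1 = 5.4%. With the SD of 9.1 from 9.1, an assumed correlation of 0.5, a 5-point difference and two-sided 0.05, power falls from 92.3% (40 pairs) to 89.3% (36 pairs). At correlation 0.7 it falls from 99.2% to 98.5%.

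**Step 4: removals, mixed model.** Var(estimates) = (Σ XᵢᵀVᵢ⁻¹Xᵢ)⁻¹, with Day 28 coded placebo, compound symmetry and intraclass correlation 0.7 to 0.9. Entries are the rise in the treatment standard error over complete data, with 2 removed and then 4 removed.

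| Data missing | Who is removed | Sequence + treatment | With visit terms |
|---|---|---|---|
| Day 140 | split evenly | 1.5–1.6%; 3.1–3.2% | 1.8–1.9%; 3.8–3.9% |
| Day 140 | all NR-first | 0.6%; 1.2–1.3% | 1.9–2.0%; 4.2–4.4% |
| Day 140 | all PBO-first | 2.5–2.6%; 5.1–5.3% | 1.9–2.0%; 4.2–4.4% |
| Days 84 and 140 | any | 2.5–2.6%; 5.1–5.3% | 2.6–2.7%; 5.4–6.1% |

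Without visit terms, an NR-first subject removed at Day 84 already has a placebo and an NR score, while a PBO-first subject has no NR score. Once visits are modelled, that difference between sequences disappears.

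**Step 5: when removal can happen.** Containers are returned at clinic visits (8.5), so the Block 1 capsule count falls at Day 84. Compliance is also assessed by telephone at Days 56 and 112 (6.1.4), so removal could come earlier. Read literally, 5.4 counts NR only. A PBO-first subject's NR count would then come at Day 140, when the scheduled RBANS is complete, and removal at Day 84 would affect NR-first subjects alone. Blinded staff cannot apply that reading. The 8.5 wording covers either product.

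**The case against.** The best defence is that this is a pilot, that 9.1 treats every outcome as exploratory, and that lead-in losses happen while everyone takes placebo. A randomised subject without an RBANS is an ordinary missing-data case, which the likelihood model handles by omission. All of that stands, and it is why the point is minor.

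The protocol also softens the removal rule. The Early Termination visit includes the RBANS, 8.4.1 implies that a subject may stop product and remain in the study, and 8.5 gives discretion. These help only in part. The visit is by invitation, and 5.4.1 ties it to withdrawal of consent, so whether a subject removed by staff receives it is not stated. After removal at Day 84 it cannot supply a second-period score. The discretion in 8.5 is what contradicts 5.4.

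The Day 0 timing rests mainly on the schedule entry: 5.3, 6.1.2 and 6.1.3 do not place randomisation, and the schema figure is not shown. The phrase in 9.1 about the onset of the trial is consistent with Day 0.

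Three stronger readings are tempting and are not supported. A reader might infer that early randomisation biases the treatment comparison materially, but Step 2 gives about 0.1 points. A reader might infer that removals hurt one sequence more. That holds only without visit terms, and 9.1 says time effects will be modelled. A reader might take the Day 84 figures as a ceiling, but earlier removal with no Early Termination RBANS costs more.

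**Conclusion.** The point holds as a minor one. As scheduled, a subject can be randomised and never measured on the primary outcome, and 5.4 as worded stops RBANS collection for a reason arising after randomisation, contrary to the intention-to-treat aim. Sections 5.4 and 8.5 contradict each other on whether removal is mandatory and on which product is counted. The passages must be reconciled, and this review does not say which rule is right.

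The lead-in part mainly costs the denominator and sequence balance. The removal part costs a little more, since it loses data after treatment has started, possibly in relation to treatment. If 2 to 4 subjects lack a Day 140 RBANS, the standard error rises by 0.6% to 5.3%, or 1.8% to 4.4% with visit terms. If only Day 28 is available, the rise is 2.5% to 5.3%, or 2.6% to 6.1% with visit terms. These figures describe precision only; any bias from treatment-related removal is not quantified.

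**What to change.** 1. Move the randomisation entry to Day 28, after lab eligibility is confirmed and the Day 28 RBANS is done, and before product is dispensed. The visit flow allows it: the RBANS is in the virtual part, up to 4 days before the office visit (6.1.3), and the pharmacy that randomises (5.3) releases product on the day of dispensing (8.1.3). Lead-in losses are not recovered. To randomise 40, 40/(1 − p) must enter the lead-in, which is 41 to 48 people at an assumed 2% to 15% loss.
2. For subjects who are non-compliant, or who stop product for non-compliance, and have not withdrawn consent, still collect the Day 84 and Day 140 RBANS. If 2 to 4 subjects are affected, this adds 2 to 4 video sessions when removal would have come at Day 84, or 4 to 8 when it would have come earlier.
3. Reconcile 5.4 with 8.5, including the product each refers to, and the Baseline wording of exclusion 10 with the Day 0 labs. This takes a few sentences.

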Assessment of normality of data distribution will be completed prior to inclusion in any analysis. If the distribution of the outcome variables (e.g., RBANS Total Score, etc) are not normal, appropriate transformations (e.g., logarithm, square-root, Box-Cox transformation, etc) will be applied. Data analysis at the individual and group levels for the primary outcome will begin with visual inspection of RBANS Total Scores at each assessment for differences from baseline for each measurement and differences between intervention conditions. Ignoring potential for carryover, a simple matched pair t-test will be performed using data from each condition. Should carryover effects or other time trends be suspected, we can use a regression model adjusting for sequence.

Mixed-effects models will be used to compare the scores at the end of each study period (Days 28, 84, and 140) between NR and PBO incorporating variance within and between participants. This within-patient level will accommodate variation resulting from the intervention crossovers as well as time effects modeled in various forms (e.g., linear and non-linear trends, carryover effects). Each within-subject regression coefficient will be treated as a random effect that can vary based on these between participant factors. The primary analysis will calculate the average intervention effect (i.e., will model the mean of the individual intervention effects as a constant). Secondary analyses will model the mean as a function of factors that vary among patients such as age and sex. These terms describe the main effects of these factors, their interactions with the intervention, and their interaction with time. The analysis will be completed using SAS PROC MIXED through a restricted maximum likelihood analysis with a mixed model with fixed effects for sequence and treatment. Appropriate covariance structure will be investigated using Akaike's information criterion (AIC).

The full multilevel model will estimate both average effects across the population of participants, as well as effects for individuals informed by the results on other participants. The predicted effects for an individual participant are weighted averages of his or her data and the averages from others. This model incorporates correlations among the measurements within an individual and enables comparison of the individual's predicted intervention effect using the multilevel model with that from using only that individual's data.

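### Section 9.1 checks normality on the outcome scores, not on the NR–PBO differences or residuals, so the primary RBANS effect can leave its point scale without a valid reason

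*Combined protocol and SAP*

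**What the plan says.** Section 9.1 names the primary endpoint: "The primary cognitive outcome measure will be the Total Scale score of the RBANS", taken at Days 28, 84 and 140. It gives two benchmarks in RBANS points. One is "a minimal detectable change in community-dwelling older adults" of 5 for the Total Score. The other is a minimum clinically important difference that "in MCI was reported to be 8 points".

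The normality rule comes before any model: "Assessment of normality of data distribution will be completed prior to inclusion in any analysis". The condition is "If the distribution of the outcome variables (e.g., RBANS Total Score, etc) are not normal, appropriate transformations", and the consequence is mandatory, from an open list ("e.g., logarithm, square-root, Box-Cox transformation, etc) will be applied").

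The analyses follow in the same section. First, "Ignoring potential for carryover, a simple matched pair t-test will be performed using data from each condition". Then comes a "restricted maximum likelihood analysis with a mixed model with fixed effects for sequence and treatment", in which within-subject coefficients are random effects and individual effects are predicted.

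The documents give no normality test or threshold, no rule for choosing among transformations, no back-transformation, and no point-scale analysis to accompany a transformed one. No check of differences or residuals is mentioned.

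**The concern.** The object tested is the score, with RBANS Total as the named example. A paired t-test does not need normal scores; it needs the within-subject differences to be roughly normal. The mixed model makes its assumptions about residuals and random effects. A check on scores can therefore err in two directions. It can trigger a transformation when the treatment comparison was sound in points, and it can pass when the differences are heavy-tailed.

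At stake is the scale of the primary result. If the rule fires, the estimate and its confidence interval are on a log, square-root or Box-Cox scale, while the plan's only yardsticks for size are 5 and 8 points. Which scale is used is settled after the data are seen.

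**Working it through.** The plan states no figure for this rule, so there is nothing to reproduce. The check has three parts.

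**Inputs from the documents.** N = 40 (section 3.1). Mean 92.4 and SD 9.1 for MCI, and benchmarks of 5 and 8 points (section 9.1). Three visits.

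**Assumptions.** Shapiro-Wilk at 5%, since the plan names no test. Within-subject correlation r = 0.8. Half SCD and half MCI, with the SCD mean 0, 12, 18 or 24 points higher, since the documents give no SCD mean. Normal within-subject errors, so the NR–PBO differences are normal by construction.

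**1. How often the check on scores fires.** Between-subject SD = 9.1 × √0.8 = 8.14. Within-subject SD = 9.1 × √0.2 = 4.07. SD of a difference = 9.1 × √(2 × 0.2) = 5.76. Ranges are over repeated runs of 3,000 to 4,000 trials:

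| SCD–MCI gap | One visit fails | At least one of three fails | Differences fail |
|---|---|---|---|
| 0 | 4–6% | 13% | about 5% |
| 12 | about 4% | 10–11% | about 5% |
| 18 | about 5% | 12–15% | about 5% |
| 24 | 13–15% | 28–32% | about 5% |

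The 13% with no mixture comes from testing three visits. Three independent tests would give 1 − 0.95³ = 14.3%, and correlation between visits lowers this slightly. Up to 18 points the mixture adds almost nothing.

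The rate depends on the assumed shape. With r from 0.7 to 0.9, at least one visit failed while the differences passed in 28–36% of trials for an 80:20 mixture with a 20-point gap, 48–74% for floor-truncated scores and 60–81% for right-skewed scores. The documents give no data on which shape applies.

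**2. The opposite error.** With normal between-subject scores and heavy-tailed within-subject errors (t, 3 df; assumed), the differences failed in about 44% of trials. In about 30% of all trials they failed while all three visits passed.

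**3. What transformation does.**

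- Inference: the rule was applied as log if any visit fails, followed by a paired t-test. Type I error was 4.2–5.4%, against 4.3–5.3% untransformed. Power at an assumed 2.5-point effect was 75–78% either way. Only the log was tested, not Box-Cox.
- Interpretation: a constant log-scale effect is a constant ratio. 8 / 92.4 = 8.7%. At a score of 80 this is 0.0866 × 80 = 6.9 points; at 115 it is 0.0866 × 115 = 10.0 points. In the other direction, the 8-point difference is ln(100.4/92.4) = 0.083 at 92.4, ln(83/75) = 0.101 at 75 and ln(118/110) = 0.070 at 110. The 5-point change is 0.053, 0.065 and 0.045 at the same scores.

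**The case against.** The strongest reply is that the rule does little damage. It is conditional, it does not select on the treatment effect, and the log version leaves error rates and power where they were. The 5- and 8-point figures are background rather than success criteria, and section 9.1 also plans visual inspection of RBANS Total Scores. The same section calls this a pilot with exploratory outcomes and no claims attached. All of that stands, and it limits the severity. It does not remove the point: the section still plans confidence intervals for the treatment difference and calls P < 0.05 significant, and an interpretable estimate is the main product of a pilot.

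A second reply also stands in part. The between-subject distribution is not irrelevant, because predicting individual effects leans on normal random effects. Nor would any residual check do. Marginal residuals from a model with sequence and treatment effects are close to the scores themselves; they failed in 7–10% of trials at gaps up to 18 points and 24–26% at 24. The fix must therefore name conditional residuals.

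A reader might infer three stronger claims that the documents do not support:

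- That mixing SCD with MCI makes the trigger likely. A balanced mixture with a moderate gap barely changes it. Much higher rates arise if all 120 scores are tested together, but that treats correlated scores as independent, and the plan proposes no such pooling.
- That the NR–PBO differences are in fact normal. The documents hold no data on this; the point is only that the rule can fire even if they are.
- That the rule distorts the test. No inferential cost was found for the log.

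**Conclusion.** The point holds as a fault in what is checked and in the scale of the result. The prespecified trigger looks at the wrong quantity for the treatment comparison and can miss the non-normality that matters. If it fires, the primary effect has no single value against the 5- and 8-point benchmarks, and the transformation is picked from an open list after seeing data. With N = 40, SD 9.1, r = 0.8 and Shapiro-Wilk at 5%, a needless trigger is expected in roughly 10–15% of trials for gaps up to 18 points and about 30% at 24, against about 5% for a check on differences. These rates rest on an assumed test, correlation and score shape. That the check is misdirected does not depend on them. Severity is minor to moderate.

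**What to change.** In section 9.1:

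- State that the primary RBANS Total analysis is in points, untransformed.
- Assess the within-subject NR–PBO differences and the conditional (within-subject) residuals of the mixed model instead of the scores. Inspect predicted random effects separately, for the individual-effect predictions only.
- If these are clearly non-normal, add a prespecified permutation test or bootstrap confidence interval on the point scale as a sensitivity analysis.
- Limit transformation to positive, skewed outcomes named in advance.

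The cost is a few sentences. No data collection, visit or sample size changes.
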